It is well known that interfascial plane blocks can result in systemic levels of LAs that achieve therapeutic concentrations (15) similar to that observed by intravenous infusions of LA (16,17). This is very likely the case for the ESP block, especially since the clinical and anatomical studies have conflicting findings regarding the loco-regional effects. Although intravenous lidocaine has shown some promise to prevent post-operative cognitive dysfunction (18,19), its effect on postoperative pain is not well studies. One study utilizing low dose lidocaine failed to show improvement in pain scores or opioid consumption, but the study did not utilize standardized multimodal analgesia

regimen (20). It is currently unknown whether the analgesic benefits of interfascial plane blocks are due to the multimodal analgesic regimen, the loco-regional benefits of the blocks, the systemic levels of local anesthetics following the block performance or a combination of all. We hypothesize that the mechanism by which the ESP block produces analgesia in the background of multimodal analgesia is probably related to the systemic absorption of local anesthetics. In addition, the safety of the ESP block using high doses of LA in cardiac surgery patients has not been rigorously assessed. We propose a pragmatic study to address both unknowns, the mechanism and safety of ESP following cardiac surgery.

III. Study Aims

- 1. The hypothesis of this study is that the analgesic effects of ESP can be attributed to its systemic distribution rather than its locoregional effects. A finding that lidocaine administered by ESP block achieves plasma concentrations in the analgesic range (2-5 ug/ml) at steady state will support our hypothesis whereas inability to reach analgesic levels will suggest that systemic distribution of local anesthetic is not a significant contributing factor of analgesia.
- 2. Despite the use of clinically acceptable doses, plasma concentrations of local anesthetic have been known to reach toxic levels following bilateral paravertebral blocks. This may also be true of ESP blocks. This study will address this concern and help establish a safety profile for ESP blocks in the cardiac patient population.

IV. Administrative Organization

University of Iowa Hospitals and Clinics—CVICU and Laboratories

V. Study Design

- i. Experimental design of the study (e.g., single-blind, double-blind): Randomized

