- ii. Study population general description: Adults undergoing elective cardiac surgery for coronary artery bypass graft (CABG) or valve surgery via sternotomy
- iii. Sample size determination and power analyses: 70 adult patients as determined using an online calculator available at: https://www.sealedenvelope.com/power/continuous-equivalence/
- iv. Study outcomes/endpoints:
 - 1. Arterial blood samples will be drawn and assessed for lidocaine concentrations
 - 2. Pain scores will be collected from EPIC electronic medical record or directly from the subjects.
 - 3. Opioid doses will be assessed and reported in morphine equivalents

VI. Study Procedures

- a. Subject selection procedures
 - i. Inclusion: Any patient >18 years and <81 years undergoing elective cardiac surgery for CABG or valve surgery via sternotomy and surgical procedure is not greater than 12 hours

Exclusion: Allergy to study medications; major livor or kidney dysfunction; BMI <20 or >50; revision surgery; Off-pump coronary artery bypass surgery; surgery via thoracotomy; narcotic dependent (opioid intake morphine equivalent > 10 mg/day for more than 3 months); other sources of chronic pain such as fibromyalgia; patients with associated significant central nervous system, liver, renal or respiratory disease; coexisting hematological disorder or deranged coagulation parameters; lack of informed consent; preoperative neurological deficits; and emergency surgery (E1, E2 and E3 classifications only).

ii. Recruitment procedures

- **1. Where will recruitment occur?** Pre-surgical clinic or Day of Surgery Admissions (DOSA)
- **2.** Where and when will consent be obtained? DOSA prior to surgery or in pre-surgical clinic
- 3. Who will obtain consent? Anesthesia team
- 4. What is the advertising plan, if applicable? N/A
- 5. What recruitment materials will be provided to the potential participant (brochures/information sheets/video presentation)? None.

iii. Screening procedures

- 1. What procedures are required for screening? Prior to the surgical procedure, the anesthesia team will review eligibility criteria: Allergic to study medication; diagnosed with major liver or kidney dysfunction; any bleeding disorders; in females verify non-pregnant state.
- 2. What is the screening schedule (number of visits, length of visits)? This will occur only on the day of surgery and will last approximately 30 minutes.

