 - Anxiolytic medications. Minimal anxiolytic medications given before surgery including midazolam given by anesthesia provider.
 - B. Intra-Operative Phase (Standard of Care At discretion of Anesthesia Provider)
 - Intraoperative opioid administration. Fentanyl IV given as needed for pain but typically < 1 mg for procedure.
 - Hydromorphone 0.5 1 mg given near completion of procedure
 - Intraoperative multimodal analgesia. If time since preoperative acetaminophen dose significantly exceeds 6 hours, acetaminophen 1000 mg IV, or via NG route is considered
 - Postoperative sedation initiated. Near the end of the procedure, dexmedetomidine or propofol infusion is begun for postoperative sedation in ICU while intubated

• All patients will receive dual post-operative nausea and vomiting (PONV) prophylaxis in the form of ondansetron and dexamethasone at appropriate time periods.

If the surgical procedure takes longer than 12 hours, the subject will be withdrawn from the study.

C. Block Performance/Procedure

• Upon arrival to the CV-ICU, patients will be assessed for eligibility to extubate based on hemodynamic and pulmonary stability on a case-by-case basis with the aim to extubate as early as possible. When appropriate, extubation will proceed following the CV-ICU Fast Track Extubation protocol that is already in place. Extubation is not required prior to the administration of study drug via IV or ESP catheters route. Participation in the study can proceed as long as after assessment by clinicians, the subject is extubated or ready to be extubated.

[figure not shown]
D. Group ESP (Study Procedures)

- Bilateral ultrasound guided erector spinae plane (ESP) catheters will be inserted either pre- or post-operatively.
- After confirming that there are no contra-indications, the subject will receive lidocaine via ESP catheter.
- Patients will receive lidocaine at a dose of 2 mg/kg ideal body weight (IBW) as bolus divided equally between the two ESP catheters.
- Subjects will then lie in a supine position.
- Lidocaine infusion via ESP catheters either through 2 dedicated pumps or via a single pump and a y-connector at a rate of 2 mg/kg/hour for approximately 48 hours.
- Blood samples will be drawn at 5, 30, 60, 120 minutes, 6 and 24 hours and assessed for lidocaine concentration.

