If an adverse/serious adverse event occurs, the study will be paused until careful evaluations is performed.

VIII. Analysis Plan

Study variables will be collected and tabulated. The continuous and discrete variables will be presented as mean and standard deviation after calculation and the categorical variables will be presented as frequencies. Normality of distribution will be assessed using Q-Q plots followed by Shapiro-Wilk test. Normally distributed data will be assessed using independent sample t-test and non-normally distributed data will be assessed using Mann-Whitney U-test. Categorical variables will be tested using chi-square tests or Fisher's exact test. Tests for equivalence will be applied for the primary outcome measures

failing which, tests of superiority will be applied. P values <0.05 will be considered statistically significant.

IX. Literature Cited

- 2. LahtinenP, Kokki H, Hynynen M. Pain after cardiacsurgery: A prospective cohort study of 1-year incidence and intensity. Anesthesiology. 2006;105 (4):794–800. doi:10.1097/00000542-200610000-00026
- 5. Reimer-Kent J. From theory to practice: preventing pain after cardiac surgery. Am J Crit Care. 2003;12(2):136–143.

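### Aim 2 asks whether ESP lidocaine reaches toxic levels, but no safety outcome or toxic threshold is named, and the planned mean and SD do not show how many patients reach high levels

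*Combined protocol and SAP*

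**What the plan says.** Section III, Aim 2, starts from the premise that "plasma concentrations of local anesthetic have been known to reach toxic levels following bilateral paravertebral blocks", says the same may be true of ESP, and concludes: "This study will address this concern and help establish a safety profile for ESP blocks in the cardiac patient population". The abstract also presents safety, in comparison with intravenous lidocaine, as something the study will evaluate.

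Section V.iv lists three outcomes:

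- "Arterial blood samples will be drawn and assessed for lidocaine concentrations"
- "Pain scores will be collected from EPIC electronic medical record or directly from the subjects"
- "Opioid doses will be assessed and reported in morphine equivalents"

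The sampling schedule in VI.d is the same in both groups: "Blood samples will be drawn at 5, 30, 60, 120 minutes, 6 and 24 hours and assessed for lidocaine concentration". The infusion runs for about 48 hours.

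Section VIII states: "The continuous and discrete variables will be presented as mean and standard deviation after calculation". Categorical variables are to be shown as frequencies and tested by chi-square or Fisher's exact test, but none is named. Arms are compared by t-test or Mann-Whitney test, and the unnamed primary outcome measures by equivalence and then superiority tests.

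The only concentration range in the documents is in Aim 1, which asks whether ESP lidocaine "achieves plasma concentrations in the analgesic range (2-5 ug/ml) at steady state". No toxic concentration is given anywhere. Section VII defines adverse and serious adverse events, routes reports to the IRB, provides for a pause if an event occurs, and says that no safety committee is in place. It describes no tabulation of events by arm.

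**The concern.** Toxicity is a matter of the upper tail: how many patients reach a high level, and how high. A mean and SD at each sampling time, with a comparison of arms, describe the centre and spread. They do not report any patient's peak or the number of patients above a given level. Equivalence of the arms would not answer the question either, because two arms can have similar means and both contain patients with high levels.

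Two things are at stake. An average inside the analgesic range could be presented as a safety profile while the share of patients above that range goes unreported. And if a cut-off is chosen only after the concentrations have been seen, the resulting count is weaker evidence than one fixed in advance.

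**Working it through.** **No planned figure to reproduce.** The documents give no expected concentration, SD, exceedance rate or safety precision. The 70 patients in V.iii come from an online calculator for equivalence of a continuous outcome. Its margin, SD and power are not stated, so that figure cannot be reproduced, and it is not a safety calculation.

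**Step 1: coverage of Aim 2.**

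| Needed for Aim 2 | V.iv | VIII |
|---|---|---|
| A defined toxic level | none | none |
| Peak level per patient | concentrations, no peak | mean and SD |
| Number of patients above a level | none | frequencies, no variable named |
| Adverse events by arm | none | frequencies, no variable named |

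**Step 2: can the mean lie inside 2-5 ug/ml while patients exceed 5?** Inputs: the bound of 5 ug/ml is from Aim 1; the means, the CVs and the log-normal shape are assumptions. For mean m and coefficient of variation CV:

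- σ = √ln(1 + CV²) and μ = ln(m) − σ²/2
- share above 5 = 1 − Φ((ln 5 − μ)/σ)

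Example, m = 3.5 and CV = 0.5: σ = √ln(1.25) = 0.472; μ = 1.253 − 0.112 = 1.141; (1.609 − 1.141)/0.472 = 0.99; share = 16.1%.

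| Mean (ug/ml) | CV 30% | CV 50% |
|---|---|---|
| 2.5 | 0.6% | 4.4% |
| 3.0 | 3.0% | 9.4% |
| 3.5 | 8.7% | 16.1% |
| 4.0 | 18.2% | 23.9% |

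All four means lie inside 2-5, yet the share above 5 runs from under 1% to about 24%. A check with another shape: at mean 3.5 and SD 1.5, where mean ± SD is exactly 2 to 5, the share above 5 is 16% under a normal distribution and 14% under a log-normal one.

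These are shares at a single sampling time. The share of patients above 5 at any of the six times cannot be smaller than the share at any one of them.

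**Step 3: precision of a count.** V.iii gives 70 in total and no allocation ratio. Assume 1:1 with all 35 ESP patients evaluable.

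- 0/35, two-sided exact 95% upper limit: 1 − 0.025^(1/35) = 10.0%
- 0/35, one-sided 95% upper limit: 1 − 0.05^(1/35) = 8.2%
- Chance of seeing no event when the true rate is 5%: 0.95^35 = 16.6%
- 5/35 (14.3%): exact 95% interval 4.8% to 30.3%

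With fewer evaluable patients, the limits are wider.

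**The case against.** The strongest reply is that the plan already has room for this. Section VIII says that study variables will be tabulated and categorical ones shown as frequencies and tested, and Section VII defines adverse events and how they are reported. An adverse-event table by arm would fit within that wording. This stands in part: it would be wrong to say the plan rules such a table out. But an analyst following the text has no named safety variable and no cut-off to count against.

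A second reply is that the SD is reported too. A mean of 3.5 with CV 50% would appear as 3.5 ± 1.75, which visibly reaches past 5. That is also fair: a careful reader would be warned. It is still not a count of patients, and with skewed data it gives only a rough idea of the tail.

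Third, the illustration depends on its inputs. At mean 2.5 the share above 5 is only about 1-4%. This stands, which is why the table includes means in the lower half of the range.

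Fourth, the protocol promises only to help establish a safety profile and calls itself a pilot in VII.iv. Limited precision is therefore not a design error; it governs how the conclusion is worded.

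A reader might infer that 9-24% of patients would have toxic levels. The documents do not support that. They present 5 ug/ml as the top of the analgesic range and never call it toxic, and they give no mean or SD from which to predict the share. Nor do they support saying that adverse events will go unreported; the gap is in the prespecified outcome and analysis.

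**Conclusion.** The concern holds as a gap in prespecification. Aim 2 poses a question about patients with high levels, V.iv names no outcome or threshold for it, and the only specified summary of concentrations is a mean and SD with a comparison of arms. The general frequency clause does not close the gap.

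Its size cannot be fixed from the documents. On the assumptions in Step 2, means that all lie inside the analgesic range leave anything from under 1% to about 24% of patients above its upper bound, so the mean alone does not answer Aim 2. The precision figures rest on 1:1 allocation and 35 evaluable ESP patients, neither of which is stated. The concentrations are being measured, so the data are not lost. What cannot be recovered after results are seen is a threshold fixed beforehand. The change should be made, but the gap does not undermine the trial as a whole.

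**What to change.** In V.iv and VIII, add the following for Aim 2:

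1. Each patient's highest measured lidocaine concentration, by arm. State whether it is total or free, since the abstract says both will be measured. State also that it covers only the 24-hour sampling window of an infusion lasting about 48 hours, so it may understate the true peak.
2. The number and share of patients above 5 ug/ml, labelled as the analgesic upper bound, and above a toxic level that the investigators specify before seeing the data, each with an exact 95% interval by arm.
3. Reported adverse events by arm, noting that they are captured through staff reports.
4. A sentence tying the safety conclusion to its precision: with 35 evaluable ESP patients, no exceedance rules out only rates above about 10% (two-sided exact 95%).

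The cost is a few lines of text and analysis, with no additional blood samples, and a somewhat more modest safety conclusion. The adverse-event comparison will be only as complete as the reporting behind it.

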- 3. Which screening tests/procedures are part of standard care and which are for research purposes only? All screening procedures listed above are part of standard of care.
- 4. What happens with screen failures (including any data gathered during screening)? A screening

log will be maintained and will be destroyed at upon study completion.

b. Randomization procedures (if applicable)

Participants will be randomized to IV or ESP groups using a computer-generated block randomization sequence and the allocation concealment will be ensured using a sealed envelope technique. The randomization sequence will be available with the PI and the research team.

c. Study Intervention

- iv. For Drug/device studies:
 - 1. Active study agents: Lidocaine
 - 2. Placebo study agents: None
 - **3. Blinding/labeling/preparation of agents:** Drug will be provided through the UIHC Investigational Drug Service
 - **4. Storage:** Room temperature. Protect from light.
 - **5. Administration:** Per study, either through ESP catheter or intravenously.
- 6. Toxicities and guidelines for adjustments: Acute emergencies from local anesthetics are generally related to high plasma levels encountered during therapeutic use of local anesthetics or to unintended subarachnoid injection of local anesthetic solution.

Management of Local Anesthetic Emergencies The first consideration is prevention best accomplished by careful and constant monitoring of cardiovascular and respiratory vital signs and the patient's state of consciousness after each local anesthetic injection. At the first sign of change, oxygen should be administered.

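### Sealed envelopes are promised for concealment, but the access rule for the randomization sequence excludes no one who screens, consents or enrols, and has no time limit

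*Combined protocol and SAP*

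**What the plan says.** Section VI.b (Randomization procedures) assigns patients to the IV or ESP arm from a computer-generated block sequence and states that "allocation concealment will be ensured using a sealed envelope technique". The sentence that follows, which closes the section, is "The randomization sequence will be available with the PI and the research team".

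Other sections bear on how that sentence works in practice:

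- **Consent (VI.a.ii):** "Who will obtain consent? Anesthesia team".
- **Screening (VI.a.iii):** before surgery, "the anesthesia team will review eligibility criteria".
- **Blinding (V.i and VI.c):** the design field reads "Experimental design of the study (e.g., single-blind, double-blind): Randomized", and the agents list gives "Placebo study agents: None". No blinding of patients, staff or assessors is described.
- **Outcomes (V.iv):** lidocaine concentrations, pain scores and opioid doses are listed. On pain, "Pain scores will be collected from EPIC electronic medical record or directly from the subjects". None of the three is named as primary.
- **Analysis (VIII):** equivalence tests are applied to the primary outcome measures.

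**The concern.** An envelope conceals an assignment only from someone who cannot see the list it was filled from. VI.b gives the list to the investigator and the research team without excluding any role and without a time limit. A person who holds the list and also approaches, screens or consents patients could foresee the next arm. That knowledge can affect, even without intent, who is approached or judged eligible.

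The eligibility criteria leave room for this. Several exclusions in VI.a.i rest on terms such as major organ dysfunction, significant disease or deranged coagulation, with no thresholds.

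At stake are the between-arm comparisons of pain scores and opioid use. With no blinding described, concealment before assignment is the main protection the plan gives them against selection.

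**Working it through.** **1. Reading the passages together.** The plan gives no figure on this point, so the main check is textual.

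| Question | What the plan states |
|---|---|
| Who holds the sequence? | The investigator and the research team (VI.b) |
| Who screens and consents? | The anesthesia team (VI.a.ii, VI.a.iii) |
| Are these groups separate? | Not stated; the research team's names are removed from the public copy |
| Is access barred before enrolment closes? | Not stated anywhere |
| When is an envelope opened? | Not stated |

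The two omissions in the access rule (no role excluded, no time limit) are therefore real. Overlap of people is left open.

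**2. What the list adds to what staff could already guess.** Block sizes are not given. If past allocations are visible and blocks are fixed with 1:1 allocation, enumerating all permuted blocks gives the share of assignments known with certainty: 50%, 33%, 25% and 20% for assumed sizes 2, 4, 6 and 8. With the sequence itself in hand the share is 100% for any size.

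**3. How large an effect could be (illustration only).** Section V.iii gives 70 patients but no margin, SD, alpha or power, so the following are assumptions: 35 per arm, one-sided 5%, 80% power, true difference zero.

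- Implied margin = (z[0.95] + z[0.90]) × √(2/35) = (1.645 + 1.282) × 0.239 = 0.70 SD.
- Let r be the correlation between the pain staff expect and the pain observed (assumed 0.3 to 0.5). Let a fraction f of candidates for the higher-pain arm be steered away, all from one end of expected pain. With f = 10% this is 10% of candidates for one arm, or about 5% of all candidates under 1:1 allocation.
- Mean shift = r × φ(z[1−f]) / (1−f). For f = 10%: 0.1755/0.90 = 0.195, so 0.0585 SD (r = 0.3) or 0.0975 SD (r = 0.5), which is 8% or 14% of the margin. For f = 5%: 0.033 or 0.054 SD, which is 5% or 8% of the margin.

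Hand check with the true difference at the margin, f = 10%, r = 0.3: 0.0585/0.239 = 0.245, and Φ(−1.645 + 0.245) = Φ(−1.40) = 8.1%. In the other direction, Φ(−1.645 − 0.245) = Φ(−1.89) = 2.9%.

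Simulation of the two one-sided tests (200,000 runs, t with 68 df), chance of concluding equivalence:

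| Scenario | r = 0.3 | r = 0.5 |
|---|---|---|
| True difference at margin, no steering | 5.0% | 5.0% |
| Highest-expected-pain 10% kept out | 8.1% | 10.9% |
| Lowest-expected-pain 10% kept out | 2.9% | 2.1% |
| Highest 5% kept out | 6.6% | 7.7% |
| Lowest 5% kept out | 3.8% | 3.1% |
| No true difference, no steering | 78.8% | 78.8% |
| No true difference, 10% steered | 78.3% | 77.2% |

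Repeat runs agree to within about 0.2 percentage points.

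**Sensitivity.** With one-sided 2.5% and 90% power the implied margin is 0.862 SD. False equivalence at the margin moves from 2.5% to 4.3% or 6.0% (highest 10% kept out), or to 1.3% or 0.9% (lowest 10% kept out).

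**The case against.** The strongest reply is that this is an ambiguity and not a failure of concealment. Someone on the study side must keep the master list, and the sentence may only say who. Sequence holders and recruiters carry different labels, and the names that would show overlap were removed from the public copy. This stands: overlap is plausible in a study run from an anesthesia service, but it is not documented. It does not remove the point, because even as a custody statement the sentence excludes no recruiting role and sets no time limit.

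A second reply is that the numbers carry little weight. Margin, SD, alpha, power, r and the steered fraction are all assumed, and the upper figures also need a true difference exactly at the margin. This stands too. The table shows the mechanism and does not set the seriousness of the point.

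A reader might go further and infer any of three things that the documents do not support:

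- **That recruiters will know the next arm.** The text permits this; nothing shows that it will happen.
- **That the trial's main equivalence conclusion is biased, or biased towards equivalence.** No endpoint is designated primary, so a link to the Section VIII test assumes that pain or opioid use is a primary outcome. The illustrated shift also runs in either direction.
- **That the lidocaine results are compromised.** No effect on concentrations is shown, and the Aim 1 criterion in Section III (an ESP plasma level of 2–5 ug/ml) is not a between-arm contrast.

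The screening log is a side issue. Section VI.a.iii says that it "log will be maintained and will be destroyed at upon study completion", which limits a later check on selective enrolment, but counts could be reported before then.

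**Conclusion.** The point holds in limited form and should be fixed. A stated access rule undercuts a stated safeguard: as written, the plan permits foreknowledge of the next arm by anyone who both holds the sequence and recruits. Confidence is high that the text contains no limit by role or time. There is no basis for saying that concealment will in fact be broken.

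The comparisons exposed are between-arm pain scores and opioid use. The size and direction of any bias are unknown. Under the stated assumptions with 10% of one arm's candidates steered, false equivalence at the margin moves from 5% to about 8–11% or to about 2–3%. If the arms truly do not differ, the chance of concluding equivalence falls by at most 1.6 percentage points (78.8% to 77.2%). The case for the change rests on the wording and its low cost, not on these figures.

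**What to change.** Replace the final sentence of VI.b with:

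> The sequence and block sizes are held by an existing person or office with no role in recruitment, eligibility or consent, and are not accessible to anyone with such a role until enrolment closes; each envelope is opened only after consent and eligibility are recorded.

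The restriction covers the investigator and any research team member who recruits. If only custody was meant, this is a clarification. The cost is protocol wording and minor custodial work for existing staff, with no extra patients or procedures.

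Optional additions: sequentially numbered, opaque envelopes, dated when opened; and de-identified counts of patients screened but not enrolled, kept before the log is destroyed.

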- Pain scores (resting and with movement/cough) will be collected from bedside record and EPIC medical record. Standard assessment protocol already in place has this charted every 2 4 hours by ICU nursing staff.
- All patients will receive continued oral multimodal analgesia
- When not eligible to receive oral medications (e.g. NPO), pain analgesia will be provided through an IV route. This can include an IV PCA pump using hydromorphone 0.2 mg with a lockout of 10 minutes and a maximum dose of 6 mg in 4 hours continued postoperatively.
- If oral medications are insufficient to provide pain relief, and the subjects are not receiving medications via PCA, pain medications

will be provided IV. • Opioid doses (both oral and IV) will be assessed and reported in morphine equivalents.

E. Group IV (Study Procedures)

- Patients will receive lidocaine at a dose of 2 mg/kg ideal body weight (IBW) through IV route.
- Subjects will then lie in a supine position.
- Lidocaine infusion via IV route at a rate of 2 mg/kg/hour for approximately 48 hours.
- Blood samples will be drawn at 5, 30, 60, 120 minutes, 6 and 24 hours and assessed for lidocaine concentration.
 - Pain scores (resting and with movement/cough) will be collected from bedside record and EPIC medical record. Standard assessment protocol already in place has this charted every 2 4 hours by ICU nursing staff
 - All patients will receive continued oral multimodal analgesia
- When not eligible to receive oral medications (e.g. NPO), pain analgesia will be provided through an IV route. This can include an IV PCA pump using hydromorphone 0.2 mg with a lockout of 10 minutes and a maximum dose of 6 mg in 4 hours continued postoperatively.
- If oral medications are insufficient to provide pain relief, and the subjects are not receiving medications via PCA, pain medications will be provided IV.
- Opioid doses (both oral and IV) will be assessed and reported in morphine equivalents.
- ii. Provide a schedule of all study assessments and subject activities, including a tabular representation or timeline as applicable

VII. Safety Monitoring Plan

i. Definition of adverse events, serious adverse events:

An adverse event (also referred to as an adverse experience) can be any unfavorable and unintended sign (e.g., an abnormal laboratory finding), symptom, or disease temporarily associated with the use of a drug, without any judgment about causality or relationship to the drug.

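### Does the lidocaine infusion need a stated weight basis, and a statement that the ESP rate is the patient total, before the trial can be interpreted?

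*Combined protocol and SAP*

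**What the plan says.** Section VI.d gives the dosing for each arm.

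- **Group ESP, bolus:** "Patients will receive lidocaine at a dose of 2 mg/kg ideal body weight (IBW) as bolus divided equally between the two ESP catheters". Both the weight basis and the split are stated.
- **Group ESP, infusion:** "Lidocaine infusion via ESP catheters either through 2 dedicated pumps or via a single pump and a y-connector at a rate of 2 mg/kg/hour", for about 48 hours. Neither the weight basis nor the split is repeated.
- **Group IV, bolus:** "Patients will receive lidocaine at a dose of 2 mg/kg ideal body weight (IBW) through IV route".
- **Group IV, infusion:** "Lidocaine infusion via IV route at a rate of 2 mg/kg/hour for approximately 48 hours". The weight basis is again not repeated.

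No other readable part of the document supplies these details. The administration entry in Section VI.c only refers back to the study procedures. No total or maximum lidocaine dose is given. A figure that could not be read stands directly before the Group ESP text, so the silence is established for the readable text only.

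Section III shows where the dose matters. Under Aim 1, a finding that ESP lidocaine "achieves plasma concentrations in the analgesic range (2-5 ug/ml) at steady state will support our hypothesis". Aim 2 is about safety, on the ground that "plasma concentrations of local anesthetic have been known to reach toxic levels following bilateral paravertebral blocks". The exclusion criteria in Section VI.a admit BMI from 20 to 50, a range over which actual and ideal weight can differ widely.

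**The concern.** The plan is exact about the small part of the dose and silent about the large part. Two consequences would follow if the silence were filled badly.

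First, if some staff used ideal weight and others actual weight, dose would vary between patients for reasons unrelated to route. If everyone used actual weight, exposure in heavier patients would rise. Aims 1 and 2 concern absolute plasma levels, so balance between the arms does not remove this effect.

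Second, if the ESP rate were set on each of two pumps, the ESP arm would receive about twice the IV dose. Route and dose would then be confounded in a trial whose purpose is to compare routes.

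**Working it through.** **1. Share of the dose given by infusion.** Inputs are the 2 mg/kg bolus and the 2 mg/kg/hour rate (Section VI.d), on one common weight basis. After T hours the share is 2T / (2 + 2T).

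| Time | Calculation | Share |
|---|---|---|
| 5 min | 0.167 / 2.167 | 8% |
| 30 min | 1 / 3 | 33% |
| 60 min | 2 / 4 | 50% |
| 120 min | 4 / 6 | 67% |
| 6 h | 12 / 14 | 86% |
| 24 h | 48 / 50 | 96% |
| 48 h | 96 / 98 | 98% |

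The 98% is correct for the full infusion, but the last listed blood sample is at 24 hours. At three of the six sampling times the bolus, whose weight basis is stated, is at least half of the dose given so far. At 6 and 24 hours, which bear most on steady state, the infusion dominates.

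**2. Patient total or per catheter.** The per-catheter reading can be tested against the ESP line itself.

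- With one pump and a y-connector, a per-catheter rate of 2 would need the pump to run at 2 x 2 = 4 mg/kg/hour. The line gives 2.
- The same rate governs both set-ups. If it meant each pump, two-pump patients would receive 4 mg/kg/hour and single-pump patients 2, so the dose within one arm would depend on the equipment used.
- The bolus is a total divided between the catheters, and the IV arm has the same bolus and the same rate.

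Only the patient-total reading makes these lines agree. Under the other reading the 48-hour ESP dose would be 2 + 192 = 194 mg/kg against 98 mg/kg, a ratio of 1.98.

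**3. Weight basis.** The documents give no ideal-weight formula, so two assumptions are shown.

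*Assumption A:* 50 kg (men) or 45.5 kg (women) plus 2.3 kg per inch over 60, for men of 160-190 cm and women of 152.4-180 cm. The lower limit for women is 60 inches, because the formula is not defined below that. At BMI 30:

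- lowest ratio of actual to ideal weight, man of 190 cm: 30 x 1.90² / 84.0 = 108.3 / 84.0 = 1.29
- highest ratio, woman of 152.4 cm: 30 x 1.524² / 45.5 = 69.7 / 45.5 = 1.53

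At BMI 50 the same two people give 180.5 / 84.0 = 2.15 and 116.1 / 45.5 = 2.55.

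*Assumption B:* ideal weight corresponds to a BMI of 21 to 25. At BMI 30 the ratio is 30/25 = 1.20 to 30/21 = 1.43. At BMI 50 it is 2.0 to 2.4.

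*Example under A:* a man of 175 cm at BMI 30 has an ideal weight of 70.5 kg and an actual weight of 91.9 kg. The rates are 2 x 70.5 = 141 and 2 x 91.9 = 184 mg/h, or 6.8 and 8.8 g over 48 hours.

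**4. Effect on the 2-5 ug/ml range.** Assume that one patient's steady-state level is proportional to the rate. At BMI 30 under A, the level on ideal weight that would become 5 on actual weight is 5/1.53 = 3.3 to 5/1.29 = 3.9. The level that would become 2 is 2/1.53 = 1.3 to 2/1.29 = 1.6. A patient could therefore cross either limit. This does not show how many patients would do so, because the documents give no distribution of levels.

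**5. Effect on the comparison of arms.** The two infusion lines are silent in the same way, and randomisation balances body size between arms on average. One rule applied to both arms multiplies dose by the same distribution of ratios in each, so it creates no systematic dose difference. A mixture of readings unrelated to arm adds variance without adding bias.

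**The case for a change.** The strongest counter-argument is that the authors thought it necessary to write both details for the bolus and omitted them for the part that delivers nearly all the drug. A 48-hour intensive-care infusion should not depend on inference, no safety committee is in place (Section VII), and one added line per arm would cost almost nothing. Aims 1 and 2 also depend on absolute exposure, which equal treatment of the arms does not protect.

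Part of this stands. The text is silent on weight basis, the two-pump wording could be tidier, and a uniform actual-weight reading would raise exposure in heavier patients. It does not follow that the plan yields a wrong result. The lines are silent and do not conflict. In each arm the infusion line comes two bullets after a bolus line that names the weight basis. The trial names one institution, and drug comes through one investigational drug service, so there is no sign in the documents that staff would read the line in different ways. Plasma lidocaine is also measured in every patient, so the range and safety questions are answered from observed levels and not inferred from the nominal dose.

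**Conclusion.** The observation is accurate, but it calls for no change to the plan. The per-catheter reading is largely ruled out by the single-pump wording, the divided bolus and the matching IV rate, so the near-doubling (1.98 times) is not a realistic threat. What remains is a qualifier missing from the infusion line in both arms. It has a natural reading within the text, and any uniform reading leaves the arms balanced.

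If actual weight were used instead of ideal weight, the rate at BMI 30 would be about 1.3 to 1.5 times higher under the assumed height-based formula, or 1.2 to 1.4 times under the reference-BMI assumption. At BMI 50 it would be about 2.0 to 2.6 times higher across both. That would change the dose to which the observed levels refer. It would not invalidate the levels or the comparison.

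The conclusion rests on three conditions: the unread figure before the Group ESP text says nothing different, one reading is used at the site for both arms, and level is proportional to rate within a patient. Nothing here says which weight basis is clinically right; that is for the investigators.
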